9.3 Populations for Analyses

Effectiveness analyses will be performed using an FAS population. Demographic and baseline

characteristics will be presented for both all participants analysis set and FAS.

The following populations are defined:

Table 3 Populations for Analysis

Population/Analysis set	Description
All Enrolled Participants	All participating patients enrolled for the study without screen failure will be included in the All Enrolled Participants population.
Full Analysis Set (FAS)	All enrolled participants with at least one non-missing post-intervention GINA guideline treatment assessment.

9.4 Statistical Analyses

The statistical analysis plan will include a more technical and detailed description of the statistical analyses described in this section. This section is a summary of the planned statistical analyses of the most important endpoints including primary and key secondary endpoints.

9.4.1 General Considerations

Unless otherwise stated, all statistical methods in the subsequent sections will be based on the following general methods.

All categorical data will be presented in contingency tables, using absolute and relative frequencies. Percentages will be rounded to the first decimal place and, therefore, may not always add up to 100%. When applicable, 95% confidence intervals (CIs) will be presented with estimates of proportions.

All continuous data will be summarized via relevant descriptive statistics, such as number of observations with available measurements, mean, standard deviation, median, first and third quartiles (Q1 and Q3) when applicable, minimum and maximum.

Missing data will not be imputed unless otherwise specified.

Missing dates or partially missing dates will be imputed conservatively for adverse events and prior or concomitant medications/procedures.

By-visit endpoints will be analyzed using observed data, unless otherwise specified. For observed data analyses, missing data will not be imputed and only the observed records will be included.

9.4.2 Effectiveness

9.4.2.1 Primary Endpoint(s)

Change from baseline in the proportion of patients with an ICS-based maintenance and/or reliever treatment at week 48

Prescription will be used to define this endpoint. The primary analysis will use mixed effect logistic regression model, taking the measurement timepoint (baseline/post-baseline) as the fixed effect, hospital, pulmonologist and patient as the random effects. In case of lack of convergency, hospital and pulmonologist factors will be removed from the model. Within the framework of this model, the 95% confidence interval and p value of the primary endpoint will be estimated and presented. The analysis will be performed in FAS.

Another sensitivity analysis will be conducted with generalized estimating equations (GEE) model using the same covariates as the primary analysis.

9.4.2.2 Secondary Endpoint(s)

Change from baseline in the proportion of participant with well-controlled asthma (ACQ-5 \leq 0.75) at week 48

The change from baseline in proportion of well-controlled asthma evaluated by ACQ-5 score at week 48 will be derived using the percentage of patients with ACQ-5 score \leq 0.75, its 95% confidence interval (95% CI) will be summarized. Normal approximation method will be used to calculate 95% CI.

Distribution of ACQ-5 total scores at week 12, 24, 36 and 48

Distribution of ACQ-5 average scores will be described using the frequency and percentage at each category listed below, a shift table will be generated wherever applicable:

Well controlled: ACQ-5 \leq 0.75

Partially controlled: 0.75 $<$ ACQ-5 $<$ 1.5

Not well-controlled: ACQ-5 \geq 1.5

Change from baseline in the proportion of participants on the treatment of ICS-formoterol as reliever at week 12, 24, 36 and 48

Change from baseline in the proportion of patients on the treatment of ICS-formoterol as reliever at week 12, 24, 36 and 48 and its 95% confidence interval (95% CI) will be summarized. Normal approximation method will be used to calculate 95% CI.

Change from baseline in ACQ-5 average score at week 12, 24, 36 and 48

The ACQ-5 overall score will be calculated as the average of the non-missing 5 symptom

questions. At least 4 out of the 5 symptom items are needed to provide an ACQ-5 overall score. Number of observations with available measurements, mean, standard deviation, median, first and third quartiles (Q1 and Q3), minimum and maximum will be presented.

Change from baseline in the proportion of participants achieving an improvement in ACQ-5 MCID of 0.5 units or more at week 12, 24, 36 and 48

Responder status will be descriptively summarized by visit as the number (%) of responders and non-responders. A responder status at post-baseline will be calculated as

- Responder: $(\text{post-baseline} - \text{baseline}) \leq -0.5$
- Non-responder: $(\text{post-baseline} - \text{baseline}) > -0.5$

Change from baseline in the proportion of participants with an ICS-based maintenance and/or reliever treatment at week 12, 24 and 36

Change from baseline in the proportion of patients with an ICS-based maintenance and/or reliever treatment at week 12, 24 and 36 and its 95% confidence interval (95% CI) will be summarized. Normal approximation method will be used to calculate 95% CI.

Asthma related treatment pattern

Asthma related treatment patterns will be evaluated by treatment distribution at baseline and at weeks of 12, 24, 36, and 48.

9.4.2.3 Exploratory Endpoint(s)

9.4.3 Subgroup Analyses

Subgroup analyses will be performed as appropriate. Any subjects with a missing value for the defined subgroup will be excluded from the analysis of that subgroup.

The subgroups to be explored may include:

- Age be category: >65 , ≥ 18 to ≤ 65 , <18
- Age of onset: <20 years old, <40 years old, ≥ 40 years old
- Phenotype of asthma: allergic or non-allergic
- Hospital Tier: Tier 2, Tier 3
- Job: related to asthma, no-related to asthma
- Baseline characteristic
- Questionnaire with response and non-response subjects
- Adherence
- Patient expectation of asthma treatment
- Asthma history information
- Asthma severity class
- Hospital Type: PCCM, non-PCCM
- Geographic region

- ICS containing change: with-to-with, with-to-without, without-to-with, without-to-without ICS containing
- ICS-formoterol as reliever: with-to-with, with-to-without, without-to-with, without-to-without ICS-formoterol as reliever

Missing data characteristics will be described in baseline characteristics, primary endpoint and secondary endpoints if applicable. The subgroups to be explored will include:

- Participants complete status: Missing at Week 48, not Missing at Week 48
- Participants complete status: Missing at Week 24, not Missing at Week 24

These analyses are exploratory and the result from these analyses will not affect the choice of terms used in the model for the primary analysis.

Other baseline variables may also be assessed if there is clinical justification.

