8.1.6.7 Patient Adherence Assessment

Adherence assessment include PDC(proportion of days covered), MPR(medication possession ratio)([Carlyne M.2022](#))and based on Medication Adherence Report Scale for Asthma, the self-assessment of adherence is developed, more details in Appendix C6, C7.

MARS-A scale consists of 10 items, which are self-reported, and each question is scored on a scale of 1 to 5. The higher the score, the better the adherence. In the end, the average score of 10 questions was taken, and a score of 4.5 or above indicated good adherence. Items have both general and asthma-specific questions. The problem statement is in a negative way. ([Jessica 19L Cohen 2009 , Yu 2014](#)) and analysis of the reasons for non-compliance with doctor's orders, the influencing factors of compliance are based on a regional compliance study design in China ([Shi, 2019](#))

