9.2 Sample Size Determination

Approximately 1500 participants will provide 80% power at a significant level of 0.05 to detect a change from baseline in the proportion of patients with an ICS-based maintenance and/or reliever treatment at week 48 of 5% (Zhao et al 2014). The baseline proportion is assumed to be 40% and a within-participants correlation is assumed to be 0.25. The proportion of missing postbaseline assessment at week 48 is assumed to be 30%.

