18. If you have a cold or flu, you should increase your asthma medication dosage (T)
19. Oral medications work just as fast as inhaled medications (F)
20. Because inhaled drugs work locally in the respiratory tract, they have fewer side effects than oral drugs. (T)
21. Asthma-relieving drugs (such as Ventolin or Terbutaline) do not work well if they are always used (T)

Condition monitoring

22. If the asthma does not have an attack, it is not necessary to visit the outpatient clinic regularly (F)
23. Regular pulmonary function tests can monitor changes in the condition (T)
24. Monitoring with a peak flow meter can provide an early indication of asthma exacerbation (T)
25. Keeping an asthma diary every day will help you know well your own condition (T)

Total 16T 9F

C 5 Patient Self-Assessment of Asthma Severity

Patient Self-Assessment of Asthma Severity

How severity level do you think your asthma is? (according to personal understanding)

A mild

B Moderate

C severe

C 6 Patient Adherence Assessment at baseline

Patient Adherence Assessment at baseline

1. Has your doctor told you that your asthma medication is for long-term use?

Yes

no

(Answer "yes", skip to 2)

2. Are the drugs you are currently using is inhaler?

Yes

no

(Answer "yes", skip to 3)

3. Please try to recall your usual medication situation. If you always agree with the following descriptions, please check "Level 1" after the corresponding description. If you do not do this at all, please check "5" level", and so on.

(1-always, 2-often, 3-sometimes, 4-rarely, 5-never)

Answer the following 10 questions

1. I only use this medicine when I need it
2. I only use it when I feel breathless
3. I decided to miss out a dose
4. I try to avoid using it
5. I forget to take it
6. I alter the dose
7. I stop taking it for a while
8. I use it as a reserve if other treatment doesn't work
9. I use it before doing something which might make me breathless
10. I take it less than instructed

4. When you were enrolled in the group, you did not take the medicine as prescribed by the doctor. What was the reason? (Multiple choice)

1. Forgetting medication, difficult to adhere to for a long time
2. The device is troublesome to use and inconvenient to carry
3. Unreasonable drug prices and unaffordable economy

4. It is troublesome to dispense the medicine, and the medicine cannot be dispensed continuously
5. Reluctance to use inhalation for a long time

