4.2.3.10 Exploratory Endpoint-10

4.2.3.11 Exploratory Endpoint-11

4.2.3.12 Exploratory Endpoint-12

4.2.3.13 Exploratory endpoint-13

4.2.4 Subgroup analyses

Subgroup analyses as below will be performed as appropriate for the primary endpoint, selected secondary endpoints and exploratory endpoints. Any subjects with a missing value for the defined subgroup will be excluded from the analysis of that subgroup. The subgroups to be explored may include as needed:

- Age by category: >65 years, ≥ 18 to ≤ 65 years, <18 years old
- Age of onset: <20 years old, <40 years old, ≥ 40 years old
- Phenotype of asthma: allergic or non-allergic
- Hospital Tier: Tier 2, Tier 3
- Job: related to asthma, no-related to asthma (occupational exposure Y or N)
- Nicotine usage frequency (current, former, never)
- Sex (Male, Female)

- BMI ($\geq 24 \text{ kg/m}^2$, $< 24 \text{ kg/m}^2$)
- Education level (elementary school and below, high school, university degree and postgraduate)
- Questionnaire with response and non-response subjects (if the subject performed ACQ and AQLQ at Visit 5 and had any questionnaire performed in each visit, the subject is defined as responder; otherwise, the subject is a non-response subject)
- Adherence (Good adherence or not)
- Patient expectation of asthma treatment
- Asthma severity class: Mild, Moderate, Severe (based on Patient Self-Assessment of Asthma Severity)
- Symptoms: Symptoms less than twice a month; Symptoms twice a month or more, but less than 4-5 days a week; Symptoms most days, or waking with asthma once a week or more; Daily symptoms, or waking with asthma once a week or more, and low lung function
- Hospital Type: PCCM, non-PCCM
- Geographic region: North, South
- ICS containing change: with-to-with, with-to-without, without-to-with, without-to-without ICS containing (From ICS containing to ICS containing, from ICS containing to no-ICS-containing, from no-ICS-containing to ICS-containing, from no-ICS containing to no-ICS-containing.)
- ICS-formoterol as reliever: with-to-with, with-to-without, without-to-with, without-to-without ICS-formoterol as reliever (From ICS-formoterol as reliever to ICS-formoterol as reliever, from ICS-formoterol as reliever to no-ICS-formoterol as reliever, from no-ICS-formoterol as reliever to ICS-formoterol as reliever, from no-ICS-formoterol as reliever to no-ICS-formoterol as reliever.)
- Participants complete status: Missing at Week 24, not Missing at Week 24.

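### The adherence subgroup can select patients on the ICS outcome itself, so its rows cannot safely be read as changes in ICS prescribing

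*Protocol*

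**What the plan says.** SAP 4.2.4 states its scope as "Subgroup analyses as below will be performed as appropriate for the primary endpoint, selected secondary endpoints and exploratory endpoints". Its list includes "Adherence (Good adherence or not", which gives two levels. Protocol 9.4.3 also lists adherence, without levels. Both documents handle an absent class in the same way: "Any subjects with a missing value for the defined subgroup will be excluded from the analysis of that subgroup".

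Protocol 8.1.6.7 names three adherence measures (PDC, MPR and MARS-A), but a cut-off is attached only to the MARS-A mean: "a score of 4.5 or above indicated good adherence". The Schedule of Activities places MARS-A at V0, V2, V3 and V5.

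The baseline form (Protocol Appendix C 6) puts two questions before the ten MARS-A items. The second is "Are the drugs you are currently using is inhaler". A printed instruction sends a yes to the items; none is printed for a no. The follow-up form (C 7) adds a third such question, on taking medication as advised.

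The primary endpoint (SAP 4.2.1.1, with visit definitions in 4.1.9) is whether an ICS-containing medicine was prescribed in the period before the visit.

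**The concern.** ICS is an inhaled treatment. A score that exists mainly for inhaler users therefore depends on something close to the endpoint. If patients without a score are dropped, those dropped at V0 are mostly patients without ICS, the only ones who can gain it. Those who remain start high and can mainly lose. With a week-48 score the selection runs the other way: those who remain end high and appear to have gained.

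An exploratory table could then show ICS prescribing falling among scored patients while the trial as a whole shows it rising, or show a gain several times the real one. If the selection acts unequally on the two rows, the difference could be mistaken for an effect of adherence. The same mechanism reaches secondary endpoint 4 (ICS at weeks 12, 24 and 36) and secondary endpoint 2 (ICS-formoterol as reliever). Its size there was not calculated.

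**Working it through.** **Inputs from Protocol 9.2.** "Approximately 1500 participants will provide 80% power at a significant level of 0.05 to detect a change from baseline" of 5 points; "The baseline proportion is assumed to be 40% and a within-participants correlation is assumed to be 0.25"; 30% missing at week 48.

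**Sample size check.** With dropout at the post-intervention visit only,

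n = (1.960 + 0.842)² × [0.40×0.60 + 0.45×0.55/0.70 − 2×0.25×√(0.40×0.60×0.45×0.55)] / 0.05² = 1481.

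The same calculation on the logit scale gives 1476. Both agree with the stated 1500, so the planning figures can be reused.

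**Joint distribution of ICS at baseline and week 48.**
- Covariance = 0.25 × √(0.40×0.60×0.45×0.55) = 0.0609.
- ICS at both visits: 0.40×0.45 + 0.0609 = 0.2409.
- ICS at baseline only: 0.40 − 0.2409 = 0.1591.
- ICS at week 48 only: 0.45 − 0.2409 = 0.2091.
- P(ICS at week 48 given ICS at baseline) = 0.2409/0.40 = 0.602.
- P(ICS at week 48 given none at baseline) = 0.2091/0.60 = 0.348.

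**Conditioning on having a score.** Assume that every ICS user is scored, and that a share s of non-ICS patients is scored regardless of their ICS status at the other visit. The documents give no value for s, so it is varied over its whole range. Loss to follow-up is left out.

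- V0 score: change = (0.2091s − 0.1591) / (0.40 + 0.60s).
- Week-48 score: change = (0.2091 − 0.1591s) / (0.45 + 0.55s).

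| s | V0 score, points | Week-48 score, points |
|---|---|---|
| 0 | −39.8 | +46.5 |
| 0.25 | −19.4 | +28.8 |
| 0.5 | −7.8 | +17.9 |
| 0.75 | −0.3 | +10.4 |
| 1 | +5.0 | +5.0 |

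These figures pool the good and not-good rows. With a V0 score the pooled sign is wrong until s reaches 0.1591/0.2091 = 0.76.

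**Checks.**
- At s = 0 with a V0 score, scored and excluded patients together return 0.40×(−39.8) + 0.60×(+34.8) = +5.0.
- With no true change (40% at both visits), the V0 and week-48 versions give −45.0 and +45.0 at s = 0, and −12.9 and +12.9 at s = 0.5. This is selection alone.
- If a score were required at both visits, the change would be 0.0 at s = 0 and +4.8 at s = 0.5, so no false fall or large false rise.

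**Split by row (illustration only).** Assume that 30% of ICS users and 5% of scored non-ICS patients have good adherence, with a V0 score and s = 0.5.
- Good row: weights 0.40×0.30 = 0.120 (ICS) and 0.60×0.5×0.05 = 0.015 (no ICS). ICS use goes from 88.9% to 57.4%, a change of −31.5 points.
- Not-good row: weights 0.280 and 0.285. ICS use goes from 49.6% to 47.4%, a change of −2.1 points.

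**The case against.** The strongest reply is that the selection is inferred. No route for a no is printed on form C 6, and where this protocol wants a questionnaire to stop, as on the COVID-19 form (C8), it says so. Treating every no as a stop would have an odd result on C 7: patients who say they did not take medication as advised would never be scored or reach the question about reasons. None of the ten items names an inhaler, so a patient on an oral asthma drug could answer them. Users of non-ICS inhalers, which appear in the Appendix E checklist, pass the inhaler question anyway. All of this raises s, and at s = 1 there is no bias in the pooled figure.

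The pairing is not fixed either. Subgroups are run as appropriate and as needed. The only visible use of the adherence split is for severe exacerbations in the interim analyses (SAP 5). PDC and MPR are also named. The SAP's exploratory endpoint sections are not legible in the public copy and may state the instrument and visit.

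Much of this stands, and it limits the size. A reader might infer that the form certainly leaves every non-inhaler patient unscored; the documents do not say so. A reader might also infer that both rows will show a large false change. The pooled figures do not show that, and the illustrative split shows one row nearly unaffected.

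Two things remain. A patient on no asthma drug has no meaningful MARS-A score whatever the form's routing, so s is unlikely to be 1. And the exclusion rule, which is stated, drops whoever is unscored. Naming a single scoring visit would settle the direction of the bias but would not remove it.

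**Conclusion.** The concern holds as a risk of selection on the outcome, not as a demonstrated false result. Against +5 points in all patients, the pooled adherence rows would show between −40 and +5 points with a V0 score, and between +46 and +5 with a week-48 score, depending on how many non-ICS patients are scored. The figures rest on the plan's 40%, 45% and 0.25, on all ICS users being scored, on MARS-A from one visit defining the class, and on an assumed s. The bias may differ between the rows and could then look like an adherence effect.

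It would be wrong to infer that the trial's main conclusion is at risk. Both documents label the subgroup analyses exploratory, and the primary FAS result is unaffected.

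**What to change.** In Protocol 9.4.3 and SAP 4.2.4:

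- State that the adherence subgroup is not applied to the ICS-prescription endpoints (primary, secondary 2 and secondary 4).
- For all other endpoints, define the class from the V0 MARS-A score. Replace exclusion by a third row, *no inhaler / MARS-A not scored*, so that the rows add up to the FAS.
- Report the number of patients with and without ICS in each row.

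The cost is two sentences, one extra table row and the loss of one exploratory table that would be hard to interpret. No new data are needed.

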9.5 Interim Analyses

There will be two interim analyses, first interim analyses will be operated for all subjects enrolled at baseline, another will happen when all subjects complete week 12 visit.

9.6 Data Monitoring Committee

No data monitoring committee is planned for this study.

10 DATA MANAGEMENT

Data management will be performed by AstraZeneca or other party.

The EDC system will be used for data collection. Trained site personnel will be responsible for entering these data into the EDC system according to data collection requirements. The eCRF Instructions will guide the study centre in performing the data entry. All entries and any changes performed will be tracked to provide an audit trail. The data will be reviewed, queried, and updated as needed.

Medical Coding will be performed using the most current version of Medical Dictionary for Regulatory Activities (MedDRA) and WHODrug™ Dictionary.

The data will be validated as defined in the Data Management Plan. Quality control procedures will be applied to each stage of data handling to ensure that all data are reliable and have been processed correctly. When all data have been coded, validated, signed, and locked, data cleaning will be completed. The final database will be locked.

11 STUDY CONDUCT AND OPERATIONAL CONSIDERATIONS

The conduct of the study and the analysis and reporting of the data shall be in accordance with all applicable laws, regulations and accepted standards.

11.1 Monitoring of the Study

AstraZeneca representatives will visit the research centre before the first subjects enter the study to:

- Discuss with the investigator (and other related researchers) their responsibilities regarding compliance with the research protocol and the duties of AstraZeneca or its representatives. These discussions will be documented in the clinical study agreement between AstraZeneca and the investigator.

During the study, an AstraZeneca representative will have regular contacts with the study site, including visits to:

- Provide information and support to the investigator(s)
- Confirm that the investigational team is adhering to the protocol, that data is being accurately and timely recorded in the eCRFs
- Perform source data verification, including verification of informed consent of participating patients. This will require direct access to all original records for each subject (e.g., clinic charts)

The AstraZeneca representative will be available between visits if the investigator(s) or other staff at the centre needs information and advice about the study conduct.

11.2 Audits and Inspections

Authorized AstraZeneca representative, a regulatory authority, an independent ethics committee (IEC), institutional review board or review board (IRB) may perform audit or inspection at the centres, including source data verification. The purpose of an audit or inspection is to systematically and independently examine all study related activities and documents, to determine whether these activities were conducted, and data were recorded, analysed, and accurately reported according to the protocol, Good Clinical Practice (GCP), guidelines of the International Conference on Harmonization (ICH), and any applicable regulatory requirements. The investigator will contact AstraZeneca immediately if contacted by a regulatory agency about an inspection at the centre.

